4.4 Subgroup Analyses

Subgroup analyses based on, but not limited to, gender, age, BMI and baseline QRS width will be provided on the primary effectiveness endpoint. These analyses will be regarded as exploratory, and have been selected for the following reasons:

- Gender The ASSURE WCD is available in two styles (male and female). Garment fit may influence false alarm performance.
- Age Higher levels of activity may be associated with higher levels of noise, and activity levels
 may be influenced by age. Subgroups will be based on a cutoff point of 75 years (<75/≥75).
- BMI Data presented previously on the LifeVest suggest that obese subjects experience a significantly higher percentage of noise, which may influence false alarm performance. (Wan C et al. ESC 2013. The impact of body mass index on wearable cardioverter defibrillator efficacy. Abstract P4926 Poster.) Subgroups will be based on a cutoff point of 30 (</≥ 30).
- QRS width Variable used for rhythm classification in the ASSURE WCD detection algorithm.
 Subgroups will be based on a cutoff of 120 ms (</≥ 120).
- ICD Device Type Subjects are eligible for enrollment with either a single or dual chamber ICD. Identification of Episode Rhythm type may be facilitated by the presence of a dual chamber ICD.

4.5 Adverse Events

All adverse events reported over the course of the study will be summarized and tabulated by category, seriousness, and relationship to the study device (possibly, probably or definitely). No formal statistical testing is planned.

5. Analysis Methods

5.1 Primary Endpoint

A random effects Poisson regression model will be fit with the number of FPAs for each patient as the outcome variable, the logarithm of days of wear as an offset term, and a random site effect. The fitted model will be used to calculate a two-sided 95% confidence interval for the FPA rate of the study device. The null hypothesis will be rejected if the upper bound of the 95% confidence interval is less than the rate reported for the comparator device (0.29). Note that a two-sided 95% confidence interval corresponds to a two-sided test with significance level 0.05 or a 1-sided test with significance level 0.025.

If the null hypothesis is rejected, the conclusion will be that the FPA rate for the WCD study device is significantly lower than the rate reported for the comparator device.

Assumptions regarding the Poisson regression model will be checked by assessing for example the deviance and goodness of fit statistics and dispersion. If substantive violations of model assumptions are suspected, a sensitivity analysis will be performed using the bootstrap method with resampling of cases. Ten thousand bootstrap samples will be created, and confidence intervals will be constructed by the percentile method. In the event there are significant violations of model assumptions for the Poisson regression model, the bootstrap confidence interval will be utilized to test the hypotheses on the primary endpoint.

An additional random effects Poisson regression model will be fit including patient characteristics (including age, gender, BMI, baseline QRS width, and ICD type) as covariates in an exploratory analysis to determine whether any of the anticipated covariates influences the estimate of FPA rate.

The primary endpoint will also be summarized as the median FPA rate, and the percentage of subjects with at least one FPA will be reported. If subjects have more than one FPA, the distribution of number of FPAs per subject may also be reported.

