4.1 Primary Endpoint

The primary endpoint is the WCD False Positive Alarm (FPA) Rate calculated as False Positive Alarms per subject-day where days per subject will be calculated by taking the total wear time in minutes as recorded in the eCRF by the Research Coordinator from the CareStation remote monitoring system divided by 1,440 minutes. The study will be considered successful if the WCD FPA Rate is less than 0.29 FPAs per subject-day.

The hypotheses to be tested are as follows:

 H_0 : $p_1 \ge 0.29^1$ H_1 : $p_1 < 0.29^1$

where

p₁ = ASSURE False Positive Alarm Rate

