4.2 Sample Size Estimation

The following assumptions were used to determine the sample size for the primary endpoint of WCD False Positive Alarm Rate:

- The primary analysis is a one-sided comparison of the WCD FPA rate per subject-day against the value of 0.29
- The WCD FPA rate is expected to be 50% lower than 0.29
- At least 90% power is considered sufficient
- The statistical test will be performed with a 2.5% significance level
- Average wear time per subject, per day, is 14 hours
- The FPA rate has a Poisson distribution with variance to mean ratio, ρ , = 14 and an intra-site correlation =0.026.²
- For large total number of expected events, the Poisson (λ) distribution is approximately normally distributed as N (μ = λ , σ^2 = $\rho^*\lambda$).

To maintain at least 90% power to detect a FPA rate 50% lower than 0.29 a sample size of approximately 105 subjects is necessary. However, the study will enroll at least 130 subjects to increase the likelihood that a subject will experience a true ventricular arrhythmic event.

Sample size calculations were performed using the R statistical package.

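### SAP 5.1 does not say which rate its site-only Poisson model tests; if it is exp(intercept), it lies about 10% below the mean rate at 0.29 and the model step's one-sided error is about 14-16%, not 2.5%

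*SAP*

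**What the plan says.** SAP 4.1 gives the endpoint as "FPA) Rate calculated as False Positive Alarms per subject-day", with days taken from recorded wear minutes, and tests it against 0.29.

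SAP 4.2 sizes the study for that quantity: "The primary analysis is a one-sided comparison of the WCD FPA rate per subject-day against the value of 0.29". The design rate is half the comparator ("The WCD FPA rate is expected to be 50% lower than 0.29"), and "The statistical test will be performed with a 2.5% significance level". It expects heavy overdispersion: "The FPA rate has a Poisson distribution with variance to mean ratio" of 14, with an intra-site correlation of 0.026.

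SAP 5.1 models each subject's alarm count with log wear-days as offset and a random site effect. There is no subject-level term, and the distribution of the site effect is not named. Then: "The fitted model will be used to calculate a two-sided 95% confidence interval for the FPA rate of the study device". The null hypothesis is rejected if the upper limit is below 0.29. Deviance, fit and dispersion are checked. If violations are judged significant, a percentile bootstrap that resamples cases decides the test. Neither the bootstrapped statistic nor the threshold for a significant violation is given.

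**The concern.** The endpoint and the 0.29 benchmark are both mean rates. In a log-link model with a normal site effect of variance s², exp(b0) is the rate at a site whose effect is zero, while the mean rate is exp(b0 + s²/2). Whenever the fitted s² is above zero, exp(b0) is the smaller of the two.

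The missing subject term enlarges the gap. Subject-to-subject variation that the Poisson likelihood cannot hold shows up as apparent variation between sites and inflates s².

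Study success rests on this single comparison. If the lower quantity is set against 0.29, a device no better than the comparator passes too often, and the reported rate looks better than the endpoint as defined.

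**Working it through.** **Inputs.** From SAP 4.2: threshold 0.29, design rate 0.145, one-sided 2.5%, variance/mean ρ = 14, ICC 0.026, and 14 hours' daily wear ("Average wear time per subject, per day, is 14 hours"). From SAP 2.1: about 30 days. From SAP 8.6: about 10 sites. With at least 130 subjects, that is 13 per site. Wear-days per subject: 30 × 14/24 = 17.5. Expected alarms per subject: μ = 0.29 × 17.5 = 5.075 at the null and 0.145 × 17.5 = 2.5375 at the design rate.

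**1. The SAP's own sample size.** On the square-root scale (not named in SAP 4.2, but it fits):

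n = [ρ/(4 × 17.5)] × (1.960 + 1.282)² / (√0.29 − √0.145)² = 0.2 × 10.507 / 0.02488 = 84.5.

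With the design effect, N = 84.5 × [1 + (N/10 − 1) × 0.026], so N = 105.4. The SAP says about 105, so the inputs are read as intended.

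**2. Size of the gap, analytically.** A site-only model sees an apparent log-scale site variance of

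s² = ln{1 + [14(1 + 12 × 0.026) − 1] / (13μ)} = ln{1 + 17.368/(13μ)}.

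- At 0.29: ln(1 + 17.368/65.975) = 0.234; exp(−0.234/2) = 0.89.
- At 0.145: ln(1 + 17.368/32.9875) = 0.423; exp(−0.423/2) = 0.81.

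True site variation alone gives ln(1 + 0.026 × 14/μ) = 0.069 and 0.134, hence ratios of 0.966 and 0.935: gaps of 3.4% and 6.5%.

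**3. Simulation at a true mean of 0.29.** Maximum likelihood with a normal site intercept and a Wald 95% interval; 2,000-4,000 trials per setting; Monte Carlo SE about 0.6 points. The base case has 10 sites of 13, gamma subject rates and lognormal site effects. The last three columns give one-sided rejection.

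| Setting | exp(b0) / crude rate | exp(b0) | exp(b0 + s²/2) | Crude rate, bootstrap by subject |
|---|---|---|---|---|
| Base | 0.895 | 14.6% | 5.4% | 7.1% |
| Gamma site effects | 0.894 | 14.2% | 5.5% | 7.2% |
| Lognormal subject rates | 0.910 | 15.9% | 7.7% | 10.4% |
| Unequal sites | 0.885 | 16.0% | 6.2% | 9.5% |
| N = 105 | 0.880 | 15.7% | 6.3% | 7.5% |
| 8 sites | 0.912 | 14.2% | 7.4% | 9.4% |
| 22 h wear | 0.931 | 12.1% | 5.5% | 7.2% |

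A t(9) quantile at 10 sites and 14 h wear lowers the exp(b0) figure to 9-11%.

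**4. What drives it.** With ICC set to zero, where median and mean sites coincide, exp(b0) is still 8.5% low and rejects in 11.6% of trials. With site variation only, it is 3.0% low and rejects in 8.6%. In a separate run of 1,500 trials per setting, the model's standard errors were kept but centred on total alarms over total days. Rejection fell from 16.2% to 7.7% (gamma subject rates) and from 16.1% to 8.7% (lognormal). The shift is thus worth 8.5 and 7.4 points. The remaining excess over 2.5%, 5.2 and 6.2 points, is not the shift; few sites and skewed counts are the likely cause.

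**5. The bootstrap route.** Simulated subject-level dispersion at 0.29 had a median near 13 (near 10 with lognormal subject rates) and never fell below 3, so the check would be expected to fail. Bootstrapping the crude rate gives the last column. Bootstrapping a refitted intercept rejected in about 42% of trials, a rough figure from 153 trials of 120 resamples each.

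**6. At the design rate.** In the base case exp(b0)/crude is 0.811, and the exp(b0) interval rejects in 98.6% of trials. Tested on the log scale, the mean rate with 130 subjects has SE = √[(14/2.5375) × 1.312/130] = 0.236, so power = Φ(0.693/0.236 − 1.960) = Φ(0.98), about 84% before any t correction.

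**The case against.** A reader might infer that the SAP commits to a median-site rate and that the trial's test therefore runs at about 16%. The documents do not support that.

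- SAP 5.1 never equates the tested rate with exp(intercept). Read with SAP 4.1, the marginal mean is at least as natural. A gamma site effect would make the intercept the log of the mean.
- The 14-16% belongs to the model step under one reading, with a normal random effect and a Wald interval. SAP 5.1 also has a dispersion check and a bootstrap that can take over, and with ρ = 14 it probably would.
- The 10-19% gap is not a difference between typical and average sites. Under the SAP's ICC that difference is 3-6%. The rest is misspecification, which the dispersion check exists to catch.
- The 19% applies at 0.145. Type I error is defined at 0.29, where the gap is about 10%.

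All of this stands, and it narrows the point. It does not remove it. The bootstrap statistic and its trigger are as open as the model's rate, and none of the SAP 5.1 routes simulated with the SAP 4.2 inputs held 2.5%: the model-implied mean gave 5.4-7.7%, the subject-level bootstrap of the crude rate 7.1-10.4%, and a refitted intercept far more.

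**Conclusion.** The concern holds in limited form. SAP 5.1 leaves the tested rate undefined and pairs it with a model that cannot hold the overdispersion assumed in SAP 4.2. Under the exp(intercept) reading, the tested quantity is about 10% too low at the null and about 19% too low at the design rate. The model-step error is then about 14-16%, or about 9-12% with a t reference or 22 h wear. The error of the whole procedure cannot be determined from the SAP, because it depends on choices the SAP does not make.

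The figures assume about 10 sites (equal in size except where stated), 30 full days of follow-up, ρ applied to each subject's total count, and gamma or lognormal subject rates. None of these distributional details is in the documents. Because the only hypothesis test is affected, this should be settled before the primary analysis.

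**What to change.** In SAP 5.1, define the tested rate as the population mean: total adjudicated false positive alarms divided by total wear days. Compute its 95% interval on the log scale with site-clustered standard errors and a t reference on (sites − 1) degrees of freedom. State that any bootstrap recomputes this same total-over-total rate, and name its resampling unit.

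State also which interval decides the test. The clustered interval does not rely on Poisson variance, so dispersion alone need not move the decision to the bootstrap. If a subject-level percentile bootstrap kept that role, the 7-10% error would remain.

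**Cost.** The change is SAP wording and a few lines of code, through the amendment route in SAP section 9. Simulated one-sided error falls to about 3-5%, still slightly above nominal. The reported rate will be higher than exp(intercept): by about 12% at 0.29 (1/0.895 = 1.12) and about 23% at 0.145 (1/0.811 = 1.23). Simulated power at 0.145 with 130 subjects is about 76-83%, below the target in SAP 4.2 ("At least 90% power is considered sufficient"). The power statements there and in the protocol's sample size section should be restated for this analysis.

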A random effects Poisson regression model will be fitted with the number of false alarms for each subject as the outcome variable. An additional random effects Poisson regression model will be fit including subject characteristics (including age, sex, height and weight) as covariates. Model assumptions will be checked, and a sensitivity analysis will be performed using the bootstrap if substantive violations of model assumptions are suspected. Further details of the statistical methods will be included in the SAP.

Analysis of Secondary Endpoints

Secondary endpoints are exploratory and do not have specific performance criteria requirements.

Summary of WCD True Positive Detections and Missed Events (False Negative Detections)

Shockable (VT/VF) events are estimated to occur at a rate of 24 per 100 patient-years based on reported appropriate shock and non-sustained VT rates in contemporary ICD trials⁵. Based on this, we estimate approximately two shockable events during the study. While all ASSURE WCD devices will be programmed to nominal settings during the study, ICD detection schemes and programmed parameters including rate threshold and duration will differ across the study population. This may be due to a variety of factors including but not limited to manufacturer, model, physician preference and unique subject conditions. Due to these differences, it is anticipated that all shockable events may not be simultaneously detected by the ICD and the ASSURE WCD. For example, it is foreseeable that the ICD may miss lower rate shockable rhythms if the ICD is programmed to a high rate cutoff (e.g. VF>200 bpm). It is also foreseeable that the

⁵ MADIT-RIT, ADVANCE III, ALTITUDE REDUCES

WCD may miss rhythms that are treated quickly by the ICD (e.g. anti-tachycardia pacing programmed) and are not sustained long enough to fulfill WCD detection criteria.

Given the anticipated low incidence of shockable events, the incidence of True Positive Detections and Missed Events for each adjudicated Episode will be summarized.

Estimated Inappropriate Shock Rate

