8.5 Control of Systematic Bias

Several measures are incorporated into the study design to help minimize bias as follows:

- This is a multi-center trial to help ensure that investigator or site or subject enrollment bias is minimized. Investigational sites are limited to enrolling no more than 18 subjects.
- Consecutively eligible subjects should be enrolled into the study to minimize selection bias.
- A Medical Monitor will review all assessments of seriousness and relatedness for adverse events, and the Medical Monitor's determinations will supersede the site-reported assessments in summaries of the data.

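### Under SAP 4.2's planning inputs the SAP 5.1 Poisson model fails its dispersion check, and the bootstrap that then decides the trial has one-sided error of about 6-12%, not 2.5%, if subjects are resampled

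*SAP*

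**What the plan says.** - **Endpoint (SAP 4.1).** The rate is "False Positive Alarms per subject-day where days per subject will be calculated by taking the total wear time in minutes", divided by 1,440. It is tested against 0.29.
- **Planning inputs (SAP 4.2).** "The FPA rate has a Poisson distribution with variance to mean ratio" 14 and an intra-site correlation of 0.026. The test is one-sided at 2.5%, daily wear is 14 hours and the expected rate is half of 0.29. "At least 90% power is considered sufficient", for which about 105 subjects are said to be needed; at least 130 are to be enrolled. Footnote 2 takes the ratio and the correlation from the sponsor's prototype study 3330766, which Protocol section 6 describes as having a 5-day wear period.
- **Primary model (SAP 5.1).** Poisson regression with "the logarithm of days of wear as an offset term, and a random site effect". There is no subject-level effect and no dispersion parameter. The null is rejected if the upper 95% limit is below 0.29.
- **Check and replacement (SAP 5.1).** Deviance, goodness of fit and dispersion are examined, with no threshold. If violations are suspected, "a sensitivity analysis will be performed using the bootstrap method with resampling of cases", with 10,000 samples and percentile limits. If the violations are significant, "the bootstrap confidence interval will be utilized to test the hypotheses on the primary endpoint".
- **Sites.** About ten (SAP 8.6). "Investigational sites are limited to enrolling no more than 18 subjects" (SAP 8.5).
- **Protocol section 12.** "a sensitivity analysis will be performed using the bootstrap if substantive violations of model assumptions are suspected"; further detail is left to the SAP.

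**The concern.** The sample size section and the analysis section describe different data. With an intra-site correlation of 0.026, nearly all the extra-Poisson variation planned in SAP 4.2 lies between subjects within a site, where a random site effect cannot absorb it. The sponsor's own planning values therefore predict that the check will fail and that the bootstrap will decide the trial.

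The bootstrap is the less fully described of the two analyses. A case could be a subject or a site, and the statistic could be the pooled rate, a model-based population-average rate, or the model intercept. On the usual reading (subjects, pooled rate) it ignores site clustering, and percentile limits cover poorly when counts are strongly right-skewed. Both faults pull the upper limit down, which favours the device.

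This is the trial's only hypothesis test, and Protocol section 6 says the study supports a premarket approval application. At stake is the chance that a device no better than the comparator is declared better.

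**Working it through.** **Inputs.** From the documents: null rate 0.29, alternative 0.145, one-sided 2.5%, ratio 14, intra-site correlation (ICC) 0.026, 130 subjects, about 10 sites, 14 h/day for about 30 days. Wear per subject is 30 × 14/24 = 17.5 subject-days. Assumed, because the documents do not give them: the shape of the count distribution, the site sizes, that cases are subjects, and that the statistic is total FPAs / total wear-days.

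**1. Reproduce the plan's 105.** The SAP does not name the scale. On the square-root scale:

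n0 = 14 × (1.96 + 1.2816)² / [4 × 17.5 × (√0.29 − √0.145)²] = 147.1 / 1.741 = 84.5.

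With design effect 1 + (n/10 − 1) × 0.026, n solves to 105.4. So SAP 4.2 does carry both overdispersion and clustering. The same formula at 130 subjects (design effect 1 + 12 × 0.026 = 1.312) gives z = 0.1577 / √(14 × 1.312 / (4 × 17.5 × 130)) = 0.1577 / 0.0449 = 3.51, and power Φ(3.51 − 1.96) = about 94%.

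**2. Does the Poisson model pass its check?** The share of variance left within sites is 1 − 0.026 = 0.974, so the average within-site ratio is 14 × 0.974 = 13.6. In simulated trials, median Pearson dispersion after fitting site effects was 10.5 with gamma subject effects, 8.1 with lognormal, and 13.3 with a zero/high two-group mixture. The lowest single-trial value at ratio 14 was 2.4. A valid model gives 1. A Pearson test at p < 0.05 failed in every trial of every scenario where it was run, including one with the ratio cut to 3.

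**3. Clustering alone.** Ignoring the design effect of 1.312 gives 1 − Φ(1.96/√1.312) = 1 − Φ(1.711) = 4.4%. At 18 per site (1 + 17 × 0.026 = 1.442) it is 5.1%.

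**4. Skewness.** Under the null the mean count is 17.5 × 0.29 = 5.075, the variance 14 × 5.075 = 71.05 and the SD 8.43, so CV = 8.43/5.075 = 1.66. A non-negative variable has skewness of at least CV − 1/CV = 1.66 − 0.60 = 1.06, so right skew is forced whatever the shape. With ICC set to 0 to isolate this cause, subject-bootstrap error was 3.3% (two-group), 5.0% (gamma) and 7.1% (lognormal).

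**5. Both together.** True rate 0.29, ratio 14, ICC 0.026, subjects resampled, pooled rate, reject if the 97.5th percentile is below 0.29:

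| Count shape | Sites | One-sided error |
|---|---|---|
| Two-group mixture | 10 × 13 | 5.9% |
| Bursts (compound Poisson) | 10 × 13 | 6.7% |
| Gamma | 10 × 13 | 8.2% (7.2-8.7% in smaller runs) |
| Gamma | uneven | 8.7% |
| Lognormal | 10 × 13 | 10.0% (9.5-10.5% in smaller runs) |
| Lognormal | 105 subjects, 10 uneven sites | 11.4% |
| Lognormal | 130 subjects, 8 uneven sites | 11.5% |

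The 8.2% and 10.0% come from 10,000 trials of 10,000 resamples each; the standard error at 8.2% is √(0.082 × 0.918/10,000) = 0.27 points. With gamma effects and milder planning values, error was 5.6% at ratio 7, 5.5% at ratio 3, and 6.8% at 22 h/day wear.

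**6. Other readings of SAP 5.1.**
- Whole sites resampled: about 6-12%.
- Subjects resampled, model refitted each time: about 5-11% for the population-average rate, and roughly 37-41% for exp(intercept), the rate at a typical site, which SAP 4.1 does not favour.
- Poisson model interval kept: about 3-9% for the population-average rate, about 12-17% for exp(intercept).
- Sites resampled, then subjects within each drawn site: about 1.5-4.7%.

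**7. Away from the boundary.** At a true rate of 0.33, subject-bootstrap rejection was 1.75% in one run, for both gamma and lognormal shapes. At 0.145 it rejected in 91-96% of trials.

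**The case against.** The SAP foresaw overdispersion: it checks for it and states in advance what replaces the model. That stands. The missing threshold is a drafting gap that adds little error by itself, because values near 10 leave little to judge.

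The size rests on shapes the documents do not give. That also stands. Clustering alone accounts for 4.4%, and the rest depends on how skewed the counts are. The ratio and ICC are planning values from a 5-day prototype study. Because the results vary so much with the reading of SAP 5.1, the firmest conclusion is that the unit and the statistic must be named.

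The remedy is not exact either: its simulated error runs up to 4.7%, and its range overlaps that of simply keeping the model's population-average interval. It reduces the error to near nominal; it does not guarantee 2.5%.

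A reader might infer more than the documents support:
- **Error up to 13%.** One scenario gave 12.6%, but it adds unequal wear and 10% early exit to lognormal effects and uneven sites. None of these is in the documents. Figures near 3-4% use ICC 0, which is not the SAP's input.
- **A conflict with the protocol.** Protocol section 12 calls the bootstrap a sensitivity analysis but leaves detail to the SAP. SAP 5.1 elaborates on it and does not contradict it.
- **That any test carrying both sources of variation must fall below 90% power.** A fixed cutoff on the pooled rate with exactly 2.5% error had power of 94.6% (gamma) and 95.4% (lognormal) at 0.145. It needs the nuisance parameters known, so it is not a usable test. It does show that the shortfall comes from estimating variance with few sites and skewed counts.

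**Conclusion.** The concern holds. Under SAP 4.2's own ratio and ICC, the SAP 5.1 model clearly fails its dispersion check and the percentile bootstrap becomes the deciding test. If it resamples subjects and uses the pooled rate, one-sided error at a true rate of 0.29 is about 6-12% against a stated 2.5%. The direction is secure: error exceeded 2.5% for every count shape tried with the pooled rate. The size is conditional on count shape, site sizes and the two planning values. None of the readings of SAP 5.1 in step 6 that use a single-stage bootstrap or keep the model interval reliably holds 2.5%.

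This is a defect of error control at the boundary, and it fades quickly above 0.29. A reader might infer that a successful result would be unsound. The documents do not show that: the plan expects 0.145, and nothing here shows that the conclusion would change there. Because this is the only confirmatory test and the correction is cheap, it should be made before analysis.

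**What to change.** Amend SAP 5.1, under SAP section 9, before the primary endpoint is analysed:

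1. Name one primary test, of the population-average rate (total FPAs / total wear-days), and remove the switch.
2. Make it a bootstrap that draws sites and then subjects within each drawn site, keeping the 10,000 samples and percentile limits. Naming whole sites as the unit is not enough.
3. Confirm its error by simulation over plausible count shapes and site sizes, and report the result.
4. Optionally add a site-cluster-robust interval on the log scale, with t limits on (sites − 1) degrees of freedom, as a sensitivity analysis. Its simulated error was about 3-6% (6.6% in one run with 105 subjects at uneven sites), so it is not an equal substitute.
5. Restate power in SAP 4.2 for the chosen test. At 0.145 with 130 subjects and 10 sites, the site-then-subject bootstrap gave about 83-86% with equal sites and 79-83% with unequal sites and wear.

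The cost is an amendment and short code, with no added subjects, visits or data. The downside is a wider interval and a stated power below the 90% in SAP 4.2. The subject bootstrap's 91-96% is not a fair benchmark, since it is obtained with inflated error.

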5.3 General Methodology

Unless otherwise stated, continuous variables will be summarized by number of observations, mean, standard deviation, median, minimum and maximum values, and categorical/dichotomous variables will be summarized using frequency tables (frequencies, percentages, confidence intervals).

Hypothesis tests of continuous variables will be based on two sample t-tests. Non-parametric Wilcoxon signed rank test may be used when underlying data are found to be non-normal.

Hypothesis tests of categorical variables will be based on a Chi-square (or Fisher exact) test.

Level of significance (α), for purposes of statistical comparisons/tests, will be 0.05.

6. Safety Evaluation

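### The exploratory covariate model in SAP 5.1 has no stated overdispersion term, and the SAP does not say that its coefficients get corrected intervals

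*SAP*

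**What the plan says.** SAP 4.2 bases the sample size on FPA counts with "variance to mean ratio, ρ , = 14 and an intra-site correlation =0.026", estimated from an earlier sponsor study.

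SAP 5.1 then proceeds in this order:

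1. The primary model is Poisson, with log wear-days as offset and a random site effect.
2. Assumptions are to be checked, with dispersion named among the checks. If violations are suspected, a case-resampling percentile bootstrap is run as a sensitivity analysis. If violations are significant, "the bootstrap confidence interval will be utilized to test the hypotheses on the primary endpoint".
3. Only after that: "An additional random effects Poisson regression model will be fit including patient characteristics". The covariates are age, gender, BMI, baseline QRS width and ICD type. The analysis is labelled exploratory, and its aim is to find out whether any of these affects the FPA rate estimate. Its random effect is not specified again.

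Protocol section 12 (Analysis of Primary Endpoint) uses a different order. It gives the primary model, then the covariate model, then the assumption check and bootstrap sensitivity analysis, and leaves further detail to the SAP.

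SAP 5.3 sets a general threshold: "Level of significance (α), for purposes of statistical comparisons/tests, will be 0.05". SAP 4.4 adds exploratory subgroup looks at largely the same factors: "Subgroup analyses based on, but not limited to, gender, age, BMI and baseline QRS width will be provided". It names no model or test for them.

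**The concern.** The SAP assumes strong overdispersion when it sizes the trial and then writes down a covariate model that leaves it out. A Poisson likelihood takes the variance of a subject's count to equal its mean, apart from what the random effects explain. The covariates differ between subjects within a site, so a random site effect with an intra-site correlation of 0.026 cannot account for between-subject variance of 14 times the mean. Standard errors for these coefficients would then be several times too small.

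At stake is whether the model can do its stated job of separating factors that affect the FPA rate from those that do not. An analyst who follows SAP 5.1 literally could report unadjusted Poisson intervals for the covariates, because the only stated use of the bootstrap interval to replace a model interval is for the primary hypothesis.

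**Working it through.** **Inputs.** Variance-to-mean ratio ρ = 14, intra-site correlation 0.026, comparator rate 0.29 and wear of 14 hours a day (SAP 4.2); about 30 days of wear and about 10 sites (Protocol section 8); at least 130 subjects (both documents). Wear-days per subject are 30 × 14/24 = 17.5. SAP 4.2 also states "The WCD FPA rate is expected to be 50% lower than 0.29", that is 0.145, so a subject is expected to have 0.145 × 17.5 = 2.54 FPAs.

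**Step 1: the plan's own sample size.** SAP 4.2 states "At least 90% power is considered sufficient" and "The statistical test will be performed with a 2.5% significance level", and arrives at about 105 subjects. A square-root-scale Poisson formula reproduces this:

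N = (1.960 + 1.282)² × 14 × DEFF / [4 × (√0.29 − √0.145)² × 17.5], with DEFF = 1 + (N/10 − 1) × 0.026.

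The solution is N = 105.4, with 89.9% power at 105. An untransformed normal approximation using both null and alternative variances gives 115.5. The enrolled 130 exceeds both. So the ratio of 14 is an active planning assumption.

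**Step 2: analytic false-flag rate.** If the true variance is ρ times the Poisson variance, the Wald statistic of a null coefficient has standard deviation √ρ instead of 1. At a nominal two-sided 5% level, P(flag) = 2 × [1 − Φ(1.96/√ρ)].

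| ρ | 1.96/√ρ | P(flag) |
|---|---|---|
| 14 | 0.524 | 60.0% |
| 10 | 0.620 | 53.5% |
| 5 | 0.877 | 38.1% |
| 2 | 1.386 | 16.6% |

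**Step 3: simulation with the random site effect.** The fitted model was Poisson with log-wear offset, random site intercept and five null subject-level covariates, with 10 sites and 500 replicates per scenario. Covariate prevalences (28%, 35%, 50%) and a 20% coefficient of variation in wear time are assumptions.

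| Count distribution | ρ | Rate | N | Mean flag rate per covariate | At least one of five |
|---|---|---|---|---|---|
| Negative binomial, form 1 | 14 | 0.145 | 130 | 57.4% | 98.2% |
| Negative binomial, form 1 | 14 | 0.29 | 130 | 58.8% | 99.0% |
| Negative binomial, form 1 | 14 | 0.145 | 105 | 57.8% | 98.2% |
| Negative binomial, form 2 | 14 | 0.145 | 130 | 57.9% | 99.4% |
| Negative binomial, form 2 | 14 | 0.29 | 130 | 62.2% | 98.8% |
| Lognormal mixture | 14 | 0.145 | 130 | 54.9% | 98.0% |
| Lognormal mixture | 14 | 0.29 | 130 | 55.8% | 97.8% |
| Negative binomial, form 1 | 5 | 0.145 | 130 | 38.1% | 90.0% |
| Near-Poisson control | 1.001 | 0.145 | 130 | 4.7% | 21.6% |

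The control holds its level, so the inflation comes from the variance assumption and not from the fitting. The last column also contains ordinary multiplicity: five independent calibrated tests would give 1 − 0.95⁵ = 22.6%.

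A separate run (400 trials per scenario, sites as fixed terms) gave 50-62% per covariate. There the true spread of the estimates was 3.1 to 3.6 times the mean reported standard error, and the Pearson dispersion was 6 to 10.

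**Step 4: what a correction achieves.** At N = 130, ρ = 14 and rate 0.145, with 300 replicates and the two negative binomial forms:

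- unadjusted: about 60%;
- standard error multiplied by the square root of the Pearson dispersion: 6-7%;
- case-resampling percentile bootstrap (200 resamples, no site effect): 7.5-8.5%;
- robust-variance Poisson: 9-10%.

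**The case against.** The strongest reply is that the plan already contains a remedy. Protocol section 12 describes both models before it calls for the assumption check and bootstrap, and its natural reading covers both. SAP 5.1 names dispersion as something to check, and with Pearson dispersion of 6 to 10 that check would very likely signal. Its first bootstrap sentence, which offers a sensitivity analysis, is not expressly limited to the primary interval. This stands. A reader might infer that the plan has no fallback at all for the covariate model, and the two documents together do not support that. What remains is that the SAP, to which the protocol defers for detail, introduces the covariate model only after the check and does not say which interval is reported for its coefficients.

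Other points that stand:

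- The model is exploratory and has no per-covariate decision rule. Flagging at 0.05 borrows the general statement in SAP 5.3, and reading it as two-sided is an assumption. The rates above apply only if unadjusted results are read in that way.
- The ratio of 14 comes from one earlier study, which Protocol section 6 describes as a 5-day study of third-generation prototypes. Here production-equivalent devices are worn for about 30 days, so the ratio may differ.
- SAP 4.4 names no model for the subgroup analyses. A reader might infer that these are misstated too, but that follows only if they are model-based.
- A reader might infer that spurious findings would reach labelling, sizing or garment design. SAP 4.4 mentions garment style only as a reason to look at gender, and neither document ties this model to such a decision.

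It could also be said that the term random effects leaves room for a subject-level effect in the covariate model. That would answer the point, but SAP 5.1 names only site.

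**Conclusion.** The point holds as a gap in the SAP's exploratory analysis. As written, the covariate model omits the overdispersion that the SAP itself plans on. At ratio 14, unadjusted Wald results read at two-sided 5% would flag each null covariate about 55-62% of the time, with standard errors too small by a factor of about 3 to 3.6. The size depends on the ratio of 14 applying to per-subject counts over about 30 days. At a ratio of 2 the rate is still about 17%, more than three times nominal.

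A reader might infer that the primary result is compromised by this model. It is not: the success criterion in SAP 4.1 and the test in SAP 5.1 do not use the covariate model, so the primary conclusion is unaffected. The change is worth making because the model would otherwise fail its stated purpose, and because SAP 5.1 and Protocol section 12 should agree on which models the check and bootstrap cover.

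**What to change.** In SAP 5.1, fit the exploratory covariate model as negative binomial with the random site effect, or as Poisson with a subject-level random intercept added to the site effect, and report intervals from that model.

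At minimum, state that the dispersion check and case-resampling bootstrap also supply the intervals for the covariate coefficients. That would bring SAP 5.1 into line with Protocol section 12, and the bootstrap result above suggests it would remove most of the inflation. Apply the same rule to subgroup rate ratios under SAP 4.4 if any are produced from a model.

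The cost is a short SAP amendment, a change of model family or an extra bootstrap step in the code, and wider exploratory intervals. The primary endpoint, sample size and conduct of the study do not change.
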